10.2.1 Primary Safety Estimand

The primary safety interest is to assess whether TEAEs occurred at least once during SC administration of CSL312 in the prophylactic treatment of pediatric subjects with C1-INH HAE during treatment from the first IP administration at Day 1 Visit through the EoT Visit or the latest available visit or event (whichever is later) for subjects without EoT Visit while subjects are allowed to treat HAE attacks with on-demand medications.

The primary safety estimand, in line with the primary safety interest of the study, follows the treatment policy strategy and is described as follows:

- Treatment condition: Q1M or Q2M treatment with 100 mg CSL312.
- Population: The target patient population, defined by eligibility criteria and who received at least 1 dose of IP (Safety Analysis Set).
- Variable: TEAEs
- ICE: The occurrence of an ICE is ignorable. All observed values will be used, regardless of occurrence of any of the following ICEs (treatment-policy strategy) :
 - Administration of on-demand medication in addition to prophylactic treatment with CSL312.
 - Prohibited concomitant medications due or not due to COVID-19 or COVID-19 vaccination.
 - Treatment adherence or early treatment discontinuation due or not due to COVID-19.
- Population-level summary: TEAE rate per subject year.

10.2.2 Analysis of Primary Safety Endpoint

Following the estimand described in [Section 10.2.1](#), the TEAEs for pediatric subjects with C1-INH HAE will be summarized by event rate per subject year using the Safety Analysis Set. All summary tables described will be presented by 100 mg Q2M, 100 mg Q1M, and overall.

In addition, TEAEs will be summarized by the number of subjects and percentage of subjects experiencing at least 1 TEAE, the number of events, as well as the event rate per injection.

For the presentation by 3-months' time windows, the TEAE will be allocated to the time window based on the TEAE start date.

An overview summary of TEAEs as well as a table by SOC and PT will be provided.

The overview summary of TEAEs will include the following:

- Any TEAE.
- TEAEs related to IP.
- TEAEs related to device issues.
- Treatment-emergent ISRs.
- Treatment-emergent ISRs related to IP.
- Treatment-emergent ISRs related to device issues.
- Temporally related TEAEs occurring within 24 hours after end of administration.
- TEAEs leading to study discontinuation.
- TEAEs leading to discontinuation of study treatment.
- TEAEs by severity and relationship to IP and to device issues.
- TEAEs by outcome.
- Treatment-emergent ISRs by severity and relationship to IP and to device issues.
- Treatment-emergent AESIs as reported by the investigator (severe hypersensitivity including anaphylaxis).
- TEAEs by SMQ search (hypersensitivity including anaphylaxis).
- Treatment-emergent AESIs and TEAEs by SMQ search (hypersensitivity including anaphylaxis) related to IP and to device issues.
- Any serious TEAEs.

To evaluate the COVID-19 impact on the primary endpoint, the overview summary of TEAEs and the summary table by SOC and PT will be repeated as a sensitivity analysis excluding all COVID-19 related TEAEs (selected by "COVID-19 (SMQ)" scope "narrow").

All AEs will be presented in a by-subject listing.

10.2.3 Analysis of Secondary Safety Endpoints

TEAEs

The following descriptive tables will be generated for TEAEs until the Follow-up Visit, including number and percentages of subjects, the number of events, and the TEAE rates per subject year of exposure and per injection:

- Overview table of TEAEs (same as described above, but until the Follow-up Visit).
- Overview table of serious TEAEs (same as described above, , but until the Follow-up Visit and restricted to serious TEAEs).
- TEAEs by SOC and PT (same as described above, but until the Follow-up Visit).
- TEAEs by SOC and PT by 3-months' time windows.
- TEAEs by SOC, PT, and severity.
- Related TEAEs by SOC and PT.
- TEAEs leading to study discontinuation by SOC and PT
- Treatment-emergent TEAEs related to clinically significant laboratory abnormalities by SOC and PT.
- Non-serious TEAEs by SOC and PT.
- Treatment-emergent AESIs and TEAEs by SMQ search (hypersensitivity including anaphylaxis) by SOC and PT.
- Related treatment-emergent AESIs and TEAEs by SMQ search (hypersensitivity including anaphylaxis) by SOC and PT.
- Serious TEAEs by SOC and PT.
- Related serious TEAEs by SOC and PT.

The following listings will be provided:

- TEAEs.
- Non-treatment-emergent AEs.
- SAEs.
- SAEs resulting in death.
- Related TEAEs.
- AEs leading to study withdrawal.
- AEs leading to permanent discontinuation of study treatment.
- AESIs and TEAEs by SMQ search (hypersensitivity including anaphylaxis).

Anti-CSL312 Antibodies

Number and percentages of subjects with total and neutralizing anti-CSL312 antibodies will be provided by study visit.

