### 1.3. Schedule of Activities

#### 1.3.1. Schedule of Assessments: Treatment Period for Subjects 2 to 5 Years of Age

Study Period		Screening Period	Treatment Period						Follow-up / Final Visit B	
Month		Up to 30 Days C		2	4	6	8	10	End of Treatment D 12	3 Months After Last Dose of CSL312
Visit Day			1	61	121	181	241	301	361	
Visit Window (Days)				± 4d E	± 4d E	± 4d E	± 4d E	± 4d E	± 4d E	± 7d
Study site visit A		X	X	X	X	X	X	X	X	X
Informed consent / IRT registration F		X								
Medical history / demographics / HAE history		X								
Inclusion / exclusion criteria		X								
Confirm eligibility for Treatment Period G			X							
Physical examination H		X	X	X	X	X	X	X	X	X
Vital signs including body weight and height I		X	X	X	X	X	X	X	X	X
Blood draws J	Hematology / biochemistry / coagulation	X			X	X		X	X	
	Pharmacokinetics / pharmacodynamics		X		X	X			X	
	Immunogenicity		X			X			X	
	Sample collection of C1-INH and C4 K	X								
Individual acute treatment plan L		X								
Diary training		X								

Study Period	Screening Period	Treatment Period							Follow-up / Final Visit B
Month	Up to 30 Days C		2	4	6	8	10	End of Treatment D 12	3 Months After Last Dose of CSL312
Visit Day		1	61	121	181	241	301	361	
Visit Window (Days)			± 4d E	± 4d E	± 4d E	± 4d E	± 4d E	± 4d E	± 7d
Open eDiary access / review eDiary instructions with subject		X							
Review eDiary data and assess / document HAE attacks			X	X	X	X	X	X	X
eDiary deactivation and collection									X
Confirm access to on-demand HAE medication M	X	X	X	X	X	X	X	X	
Prior medications and treatment	X								
Dispensation of IP via IRT		X	X	X	X	X	X		
Accountability of IP			X	X	X	X	X	X	
Administration of IP at site N		X O	X	X	X	X	X		
Concomitant medications									
Adverse events									

C1-INH = C1-esterase inhibitor; d = days; eDiary = electronic Diary; HAE = hereditary angioedema; IP = investigational product; IRT = Interactive Response Technology; PD = pharmacodynamic(s); PK = pharmacokinetic(s); SC = subcutaneous.

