### 3. OBJECTIVES AND ENDPOINTS

**Table 2: Objectives and Endpoints**

Objective	Endpoint	Summary Measure
Primary		
The primary objectives of the study are to evaluate the safety and PK of SC administration of CSL312 in the prophylactic treatment of pediatric subjects with C1-INH HAE.	TEAEs	Number of subjects, percentage of subjects, and number of events as well as the event rates per injection and per subject year
	PK parameters after SC administration of CSL312 at steady state: 
 
• <math>C_{max}</math>
 
• <math>C_{trough}</math>
 
• <math>T_{max}</math>
 
	
 
• Mean (SD) and geometric mean (geometric CV%) for all PK parameters except for <math>T_{max}</math>
 
• Median (minimum, maximum) for <math>T_{max}</math>
 

Secondary		
The secondary objectives of this study are to evaluate efficacy, PD, and safety of CSL312 in the prophylactic treatment of pediatric subjects with C1-INH HAE.	
 
• Time-normalized number of HAE attacks
 
• Time-normalized number of HAE attacks treated with on-demand treatment
 
• Time-normalized number of moderate and / or severe HAE attacks
 
• Percentage reduction in the time-normalized number of HAE attacks
 
	
 
• The time-normalized number (per month and year) of HAE attacks, of HAE attacks treated with on-demand treatment, and of moderate and / or severe attacks on treatment, respectively
 
• The percentage reduction and the number of subjects experiencing at least <math>\geq 50\%</math>, <math>\geq 70\%</math>, <math>\geq 90\%</math>, or equal to 100% (attack-free) reduction in the time-normalized number of HAE attacks on treatment compared to their time-normalized number of HAE attacks documented in medical records
 

Objective	Endpoint	Summary Measure
	
 
• SAEs
 
• Deaths
 
• Related TEAEs
 
• TEAEs leading to study discontinuation
 
• TEAEs in each severity category
 
• Anti-CSL312 antibodies
 
• Laboratory findings reported as AEs
 
• AESIs (severe hypersensitivity including anaphylaxis)
 
	The number and percentage of subjects experiencing the specified safety events on treatment as well as the event rates per injection and per subject year

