3.5.1 Independent Data Monitoring Committee

An Independent Data Monitoring Committee (IDMC) will be established to monitor the efficacy and safety data generated during the study. The IDMC will consist of independent clinical specialists in HAE, who also have experience in clinical trials. The IDMC will review accumulating data from the ongoing study. Based on these reviews, the IDMC will advise on the further conduct of the study. No success or futility thresholds will be set for the IDMC reviews. The Sponsor will continue the study unless a safety issue is confirmed that warrants study termination. The composition, activities, analyses, responsibilities, and timing of meetings of the IDMC will be described in the IDMC charter.

The following outputs are planned for IDMC meeting #2:

1. Tables:
 - i. Demographic Characteristics
 - ii. HAE History
 - iii. Time-normalized Number of HAE Attacks During Various Time Windows of the Treatment Period
 - iv. Analysis of Responders
 - v. Overview of Treatment-emergent Adverse Events
 - vi. Overview of Serious Treatment-emergent Adverse Events
 - vii. Treatment-emergent Adverse Events by System Organ Class and Preferred Term

2. Figures:

- i. Subject Profiles for Study Participation, HAE Attacks by Severity, and On-demand Treatment

3. Listings:

- i. HAE Attacks – Investigator Reported
- ii. Derived Efficacy Variables: Time-normalized Number of HAE Attacks and Percent Reduction
- iii. Treatment-emergent Adverse Events

The IDMC mock TLF shells are provided in a separate supporting document.

In subsequent IDMC meetings, outputs may be added or removed including PK concentration listings and summaries.

4 Changes from the Protocol Planned Analyses

No changes to the analyses as presented in the study protocol are currently planned. Any changes in the planned analysis will be described in a new version of the SAP or in the CSR.

5 Study Analysis Sets

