10.3 Clinical Laboratory Evaluations

Laboratory tests will be summarized descriptively in standard units by scheduled visit for each dosing regimen and overall. For continuous laboratory tests, descriptive statistics for the measured values and for change from Baseline will be presented. For definition of the Baseline assessment see [Section 7.2.3](#). Categorical laboratory tests will be summarized by number and percentage of subjects in the respective categories (based on the Safety Analysis Set with non-missing values at each visit). Summary tables will be provided for hematology, biochemistry, and coagulation.

All laboratory test results (scheduled and unscheduled) will be listed. By-subject listings for hematology, biochemistry, coagulation, and immunogenicity will be provided. Comments to the laboratory test may be provided in a separate listing, if applicable and if the comment is too long to fit into the column width of the general listing.

A by-subject listing for laboratory abnormalities will be provided in the same format as the laboratory listings described above only including abnormal laboratory results.

The number and percentage of subjects with clinically significant laboratory findings related to a TEAE will be summarized by laboratory test. Those will be identified through the eCRF 'Clinical Significant Safety Lab Data.' Percentages will be based on the Safety Analysis Set with non-missing values at each visit.

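### The planned antibody tables count positives visit by visit, so the number of children ever or newly positive for anti-CSL312 antibodies on treatment cannot be read from them

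*SAP*

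**What the plan says.** Protocol Table 2 lists "Anti-CSL312 antibodies" among eight secondary safety endpoints that share one summary measure: "The number and percentage of subjects experiencing the specified safety events on treatment as well as the event rates per injection and per subject year". SAP Table 2 (SAP Section 3.1) repeats that measure in the same words.

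The analysis text is narrower. SAP 10.2.3 gives one sentence on antibodies: "Number and percentages of subjects with total and neutralizing anti-CSL312 antibodies will be provided by study visit". SAP 10.3 adds a listing, "By-subject listings for hematology, biochemistry, coagulation, and immunogenicity will be provided", but immunogenicity is absent from its summary tables: "Summary tables will be provided for hematology, biochemistry, and coagulation".

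Both schedules of assessments (Protocol 1.3.1 and 1.3.2) mark the "Immunogenicity" row at Day 1, Month 6 and Month 12 / End of Treatment only. SAP 7.2.5 keeps unscheduled results out of by-visit summaries. SAP Section 4 states: "No changes to the analyses as presented in the study protocol are currently planned".

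**The concern.** A child-level measure over the treatment period and a set of visit-level counts are different quantities. The first asks how many children had antibodies at some point on treatment. The second asks how many were positive on each sampling day. The second does not determine the first, because it does not show whether the positives at Month 6 and at End of Treatment are the same children. Nor does it show whether a child positive at a later visit was already positive at Day 1.

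Immunogenicity is one of the two potential risks in Protocol Table 1, and the mitigation given there is to monitor the development of antibodies over the study. Development is a within-child change. If the counting rules are not written down, the treatment of Day 1 positives, missing Day 1 samples, unscheduled samples and the denominator would be settled after the data are seen. With about 20 children, each child is worth 1/20 = 5 percentage points.

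**Working it through.** The plan states no antibody rate and no sample size calculation, so there is no figure of its own to reproduce. The check has two parts.

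**1. Required measure against planned output**

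| Element of the Table 2 measure | Planned for antibodies? |
|---|---|
| n (%) of children with the event on treatment | At single visits only (SAP 10.2.3) |
| Rule for positive at any time on treatment | None found |
| Rate per injection, rate per subject year | Not specified for antibodies |
| By-subject data | Listing (SAP 10.3) |

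SAP 7.2.3 defines Baseline as the last value before first dose, but the antibody summary does not use it.

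**2. How far by-visit counts fix the on-treatment count**

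Inputs: two scheduled samples after Day 1 (Protocol 1.3.1 and 1.3.2), and n = 20 enrolled or n = 15 completing (SAP Section 3). The positive counts a (Month 6) and b (End of Treatment) are assumed. All n children are taken to have both samples, with no unscheduled positives.

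Let E be the number of children positive at one or both visits. Full overlap gives the lower limit and no overlap the upper:

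max(a, b) ≤ E ≤ min(n, a + b)

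| n | a, b | E | Percentage |
|---|---|---|---|
| 20 | 1, 1 | 1 to 2 | 5.0 to 10.0 |
| 20 | 2, 2 | 2 to 4 | 10.0 to 20.0 |
| 20 | 3, 3 | 3 to 6 | 15.0 to 30.0 |
| 15 | 2, 2 | 2 to 4 | 13.3 to 26.7 |

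For n = 20 the Wilson 95% limits are 2.8% to 30.1% for 2 children and 8.1% to 41.6% for 4. These intervals overlap widely. The problem is therefore not precision: the same by-visit table is compatible with either point estimate.

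**Adding Day 1.** Suppose 1 of 20 is positive at Day 1 and 2 are positive at each later visit.
- Fewest newly positive: the Day 1 positive child stays positive at both visits, and one other child is positive at both. Newly positive = 1.
- Most newly positive: the Day 1 positive child is negative afterwards, and four different children are positive once each. Newly positive = 4.

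The same three rows (1, 2, 2) thus allow 1 to 4 newly positive children. Listing every pattern of results consistent with those rows gives the same range.

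An unscheduled positive in a child negative at both scheduled visits would raise the true count above what the table can show, because SAP 7.2.5 leaves it out.

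**The case against.** The case for leaving the plan alone has several sound parts.

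- **The data are not lost.** SAP 10.3 lists all laboratory results, scheduled and unscheduled. With 20 children and three scheduled samples each there are 20 × 3 = 60 scheduled results, so a hand count is easy. This stands, but a hand count is not a prespecified summary and its rules are unwritten.
- **The Month 6 and End of Treatment rows are on-treatment percentages.** This also stands. A reader might infer that nothing is produced for this endpoint; that goes too far. What is missing is the count across visits.
- **Day 1 has its own row.** A reader might infer that pre-existing positivity is counted as an effect of the drug. SAP 10.2.3 does not pool Day 1 with later visits or label any row treatment-emergent, so the documents do not support that.
- **The Table 2 cell is generic.** It serves eight endpoints and does not mention ever-positive or treatment-emergent antibodies. Positive at any time on treatment is the more natural reading of an on-treatment number of subjects, but it is a reading. Counting the newly positive is a sensible addition that the protocol does not explicitly require.
- **An undeclared departure from a protocol analysis?** A reader might infer this from SAP Section 4. Protocol Section 9 describes no antibody analysis, and Protocol 9.4.3 leaves other safety assessments to the SAP. The mismatch is with Table 2, including the SAP's own.
- **The size is hypothetical.** Protocol Table 1 describes the immunogenicity risk to date as low, and the doubling needs no overlap between the two visits. With full overlap there is no understatement.

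The mock tables are a separate document (SAP Section 2) and were not available. They may contain a row for any post-dose positive, but the SAP text would still lack the derivation.

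**Conclusion.** The concern holds as a mismatch between the summary measure in Table 2 of both documents and the single by-visit summary in SAP 10.2.3. No summary described in the SAP gives the number of children ever positive or newly positive on treatment. With assumed counts of 2 of 20 at each of Month 6 and End of Treatment, the on-treatment figure is undetermined between 10% and 20%. With one Day 1 positive as well, the newly positive count is undetermined between 1 and 4. These ranges rest on assumed counts and complete sampling. They show what the table leaves open and do not predict a result.

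The Table 2 rates per injection and per subject year are also left open for antibodies. They suit a status sampled at three visits poorly, so saying that they do not apply may be the right answer. No primary endpoint and no data collection is affected. It is worth settling before database lock.

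**What to change.** Add to SAP 10.2.3, for total and for neutralizing antibodies, by regimen and overall:

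- (a) n (%) of children positive at any sample after the first dose, unscheduled samples included, among children with at least one post-dose sample;
- (b) n (%) newly positive among children with a negative Day 1 sample. Show children positive at Day 1 and children with no Day 1 sample on separate lines; a missing Day 1 result should not be counted as negative.

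Keep the by-visit table. State whether the Table 2 rates per injection and per subject year apply to antibodies and, if so, define them. A confidence interval is optional in this descriptive study.

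Cost: a paragraph of SAP wording and a few table rows. No extra blood sampling or protocol visit is needed.

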10.3 Clinical Laboratory Evaluations

Laboratory tests will be summarized descriptively in standard units by scheduled visit for each dosing regimen and overall. For continuous laboratory tests, descriptive statistics for the measured values and for change from Baseline will be presented. For definition of the Baseline assessment see [Section 7.2.3](#). Categorical laboratory tests will be summarized by number and percentage of subjects in the respective categories (based on the Safety Analysis Set with non-missing values at each visit). Summary tables will be provided for hematology, biochemistry, and coagulation.

All laboratory test results (scheduled and unscheduled) will be listed. By-subject listings for hematology, biochemistry, coagulation, and immunogenicity will be provided. Comments to the laboratory test may be provided in a separate listing, if applicable and if the comment is too long to fit into the column width of the general listing.

A by-subject listing for laboratory abnormalities will be provided in the same format as the laboratory listings described above only including abnormal laboratory results.

The number and percentage of subjects with clinically significant laboratory findings related to a TEAE will be summarized by laboratory test. Those will be identified through the eCRF 'Clinical Significant Safety Lab Data.' Percentages will be based on the Safety Analysis Set with non-missing values at each visit.

10.4 Other Safety Measures

10.4.1 Vital Signs

Systolic and diastolic blood pressure, respiratory rate, pulse rate, and temperature including body weight and height will be collected as vital signs. BMI will be derived at the visits when height or weight are assessed. No change from Baseline will be calculated for weight.

Vital signs will be presented in standard units and in alphabetical order. Descriptive statistics for vital signs at each scheduled visits and change from Baseline (see [Section 7.2.4](#)) will be provided.

A by-subject listing for vital signs results and change from Baseline for each visit (scheduled and unscheduled) with visit date and time will be provided.

10.4.2 Physical Examination

Date and time of performed physical examinations will be listed only.

11 Pharmacokinetic Analyses

The PK analysis will be performed using the PK Analysis Set. PK parameters after SC administration of CSL312 at steady-state (C_{\max} , C_{trough} , and T_{\max}) are one of the two primary endpoints in this study.

All non-compartmental analyses are to be performed according to CSL guideline for conducting non-compartmental pharmacokinetic analysis and will be performed by CSL Behring Clinical Pharmacology and Pharmacometrics (CPP) or their designate.

The External Service Provider (ESP) for Statistical Programming and Biostatistics will receive SDTM data including PC and PP domain from CSL. The PC and PP process will be according to CSL guidelines.

11.1 Drug Concentration Measures

Handling of PK concentration data and imputation of below limit of quantification (BLQ) values for noncompartmental analyses will be performed according to the CSL guideline for conducting non-compartmental pharmacokinetic analysis. Plasma concentrations of CSL312 will be summarized by nominal time points and dosing regimen (100 mg Q2M and 100 mg Q1M). Plasma concentrations will be summarized with descriptive statistics: number of observations, i.e., values $>$ lower limit of quantification (LLOQ) plus values below limit of quantification (BLQ), number and percentage of BLQ values, with percentage BLQ values being calculated as $100 * \text{number of values BLQ} / \text{number of observations}$, mean, SD, CV%, median, minimum, maximum, Q1 and Q3, geometric mean and its respective 90% CI, and geometric CV%.

The geometric statistics will be using (natural) log-transformation of the plasma concentration data. The CV% will be expressed as a percentage. It will be calculated as $100 * \sqrt{\exp(\text{SD}_{\log}^2) - 1}$ with SD_{\log} being the SD of the log-transformed data. The geometric mean and its two-sided 90% CI will be calculated as the arithmetic mean and the lower and upper limits of the two-sided 90% Wald CI of the log-transformed data, and subsequently back-transforming the mean and the lower and upper confidence limits.

For summary statistics, calculation of mean concentrations at any individual time points are performed if at least 50% of the individual values are available with measurement values $>$ LLOQ (i.e., are quantifiable); else reports as NC.

The imputation rules below will be used for summary statistics of CSL312 plasma concentrations.

- The sampling time of pre-dose samples relative to start of the dose will be treated as 0.
- Concentration values below LLOQ in pre-dose samples and in samples taken before the time of the first quantifiable concentration will be treated as 0.
- Post-dose BLQ concentrations flanked by quantifiable concentrations will be set to missing.
- If 2 or more BLQ concentrations occur in succession, the profile will be considered to have terminated the quantifiable concentration prior to the 2 consecutive BLQs. All subsequent values will be treated as missing.
- Post-dose BLQ concentrations after the last quantifiable point will be set to missing for summary statistics of plasma concentrations.
- Mean or median values of 0 will be included in summary tables.

The LLOQ for CSL312 will be documented in the PK assay validation report to be provided prior to DBL.

Mean (\pm SD) CSL312 concentrations versus nominal sampling time point will be plotted on linear and semi-logarithmic scales by dosing regimen.

Individual concentration-time plots will be presented by actual sampling time point on linear and semi-logarithmic scale.

CSL312 plasma concentrations will be listed by subject, including actual sampling date and time, nominal time point and actual time from end of previous injection. Concentrations that are BLQ will be reported as "<LLOQ" in the by-subject listings.

Any plasma concentration data excluded from the derivation of PK parameters will be flagged. These data will be included in the relevant data listings, with a footnote to indicate that these values have been excluded in the PK analysis.

Time deviations from scheduled sampling time points and its impact on the PK parameter derivation will be discussed during the PARM. PK parameter derivation will be based on actual sampling time.

